6.3 Quality of life endpoints

• Change from baseline by visit up to Week 108 in SF-36v2[™] Health Survey domain and component scores.

6.4 Pharmacoeconomic endpoints

- Change from baseline by visit up to Week 108 in WPAI:MS scores
- Health care resource utilization from baseline up to Week 108 (number of hospitalizations, length of stay, number of intensive care admissions for MS relapse and visits to an emergency medical services facility for MS)

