If a secondary endpoint listed as part of the fallback procedure above is successful, the preserved alpha is passed along to the next secondary endpoint in the sequence and the summed alpha is used for testing that endpoint. Thus, as sequential tests are successful, the alpha accumulates for the endpoints later in the sequence; these endpoints are then potentially tested with a progressively larger alpha, but always with at least 1/3 of the alpha.

In a last step, the secondary endpoint

• Time to 24-week CDA from baseline to EOS [24-week CDA]

is tested in a subsequent stage following Time to 12-week CDA with the remaining alpha.

A graphical description of this testing strategy for the primary and secondary endpoints following the approach from Bretz, et al. [Bretz 2009] is provided in Figure 8 Overall testing strategy.

Based on the latest published information from recent MS trials, the disability accumulation rate is expected to be lower than assumed in earlier protocol versions [Cohen 2018, Comi 2018]. This results in a lower than anticipated probability of the study providing a robust evaluation of the effect of ponesimod on disability accumulation and, consequently, would have limited the ability to assess the other secondary endpoints with the previously planned hierarchical multiple testing strategy. The sponsor considers that the introduced fallback type multiple testing strategy optimizes the ability of the trial to obtain conclusive results on key disease parameters.

Analyses for secondary endpoints will be conducted at an overall two-sided 5% alpha level, with multiplicity adjustment as per the above testing strategy. 95% confidence intervals will be presented. The statistical analyses sections and sample size calculations for the secondary endpoints have been updated accordingly.

Additional minor changes and clarifications were made to the protocol as follows:

- Cladribine was added to the list of orally administered disease-modifying therapies.
- It was clarified that oral taper of corticosteroids should not be administered in order to harmonize the treatment of relapses in the study and to minimize the risk of combined immunosuppression.
- It was clarified that No evidence of disease activity (NEDA) status will be considered up to EOS.
- It was corrected that health care utilization will be not be displayed by visit.

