 For subjects who enter the extension study, the FU period starts after the last dose of study drug and ends with a safety FU visit (FU1) 14–22 days after the last dose of study drug or with an abbreviated FU2 23–37 days after the last dose of study drug (if compliance to the teriflunomide accelerated elimination procedure was assessed as not sufficient at FU1). For subjects who do not enter the extension study, the safety FU period lasts for 30 days after the last dose of study drug and includes two safety FU visits (FU1, FU2) at 14–22 and 30–37 days after the last dose of study drug, respectively.
Post-treatment observation period (PTOP): Subjects who prematurely discontinue study treatment will enter the PTOP which lasts until 108 weeks after randomization (i.e., planned EOT period). It consists of an abbreviated schedule of assessments at the time of the originally scheduled 12-weekly visits.
 End-of-Study (EOS) EOS is reached when treatment, safety FU, and, if applicable, PTOP have been completed. For subjects who completed the 108-week treatment period and enter the extension study, the EOS visit corresponds to the FU visit (FU1) conducted 14–22 days after the last study drug dose or to the abbreviated FU2 visit conducted 23–37 days after the last study drug dose (if needed for compliance reasons with the teriflunomide accelerated elimination procedure).

5 December 2018, page 33/376

	• For all other subjects, the EOS visit corresponds to the 30-day FU visit (FU2) or to the last visit of PTOP (i.e., Week 108 Visit of the PTOP), whichever is last.
PLANNED DURATION	Approximately 171 weeks (3.3 years) from first subject first visit to last subject last visit.
	For an individual subject, the maximum duration of the study will be approximately 118 weeks (2.2 years).
SITE(S) / COUNTRY(IES)	Approximately 200 sites in 25 countries in North America, South America, Eastern and Western Europe, Pacific (planned).
SUBJECTS / GROUPS	Approximately 1100 subjects will be randomized in 2 groups in a 1:1 ratio to receive ponesimod 20 mg (approximately 550 subjects) or teriflunomide 14 mg (approximately 550 subjects).
	Randomization will be stratified by prior use of MS disease-modifying treatment in the last two years prior to randomization (yes, no) and by baseline Expanded Disability Status Scale (EDSS) score (EDSS \leq 3.5, EDSS $>$ 3.5).

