Periods		PRE-RANDC	MIZATION									
	Name	(1	(1)		TREATMENT PERIOD							
	Duration	Up to 4	5 Days	108 Weeks								
Visits	Number	1	2	3	4	5	6	7	8-9	10		
	Name	Screening	Baseline	Rand	W2	W4	W12	W24	W36 - 48	W60		
	Time	Day -4	5 to -1	Day 1	Day 15	Week 4	Week 12	Week 24	Week 36 – 48	Week 60		
	Visit window			-	$\pm 1 \text{ day}$	$\pm 3 \text{ days}$	\pm 7 days	\pm 7 days	\pm 7 days	\pm 7 days		
Informed conso	ent*	Х				2			, i i i i i i i i i i i i i i i i i i i	· · · ·		
Inclusion/exclu	usion criteria*	Х	Х	Х								
Demographics	*	Х										
Medical histor	y / smoking status*	Х	Х									
MS history & t	treatment*	Х										
McDonald crit	eria (revision 2010)	Х										
EDSS/FS*	· · ·	Х	Х				Х	Х	Х	Х		
Relapse* (2)	Relapse* (2)		Х	X (2) <						> X (2)		
MSFC*, SDM	Т *	X(3)	X(3)	X(3)			Х	Х		Х		
FSIQ-RMS**	(4), PGI-S**, CGI-C*		X(5)				Х	Х		Х		
SF-36v2**			Х				Х	Х		Х		
Health care resource utilization* (6)					Х	Х	Х	Х	Х	Х		
WPAI:MS**			Х				Х	Х		Х		
Patient prefere	nce questionnaire** (7)	Х	Х									
Chest X-ray* ((8)	Х										
eC-SSRS**			Х							Х		
MRI** (9)			Х							Х		
Concomitant m	nedications*	Х	Х	Х	Х	Х	Х	Х	Х	Х		
Physical exami	ination*	Х	Х			Х	Х	Х		Х		
Dermatologica	l examination* (10)		Х							Х		
Body weight a	nd height* (11)	Х								Х		
Body temperat	ure*	Х	Х	Х	Х	Х	Х	Х	Х	Х		
SBP/DBP*		Х	Х	X(12)	Х	Х	Х	Х	Х	Х		
12-lead ECG**	* (13)	х	Х	X(14)	Х	х	X(15)	Х	Х	Х		
Ophthalmologi	ical examination* / OCT* (16)	Х					Х	Х		Х		
PFT** (17)			Х			Х	Х			Х		
Hematology/C	hemistry** (fasted)	Х	Х		Х	X (1	8) <>	· X (18)	Х	Х		
Urinalysis		Х				Х	Х	Х		Х		
Tuberculosis te	est / Viral serology **	Х										
Additional seru	um sample for viral serology		Х									
Pregnancy test	*/**	X (19)	Х		Х	Х	Х	Х	Х	Х		
PK sampling for	or ponesimod* (20)			х			Х			Х		
Study drug dis	pensing & accountability											
(21)*/**				Х	Х	Х	Х	Х	Х	Х		

Ponesimod / ACT-128800 Relapsing multiple sclerosis Protocol AC-058B301, OPTIMUM Version 7 5 December 2018, page 46/376

Confidential

Study drug swallowing test (optional)		Х							
AEs*/SAEs(22)	Х	Х	Х	Х	Х	Х	Х	Х	Х

*Data collected in the eCRF

**Data electronically transferred to sponsor.

Day 1 (date of randomization visit) is to be used as the reference date for the purpose of calculating the subsequent visit dates (and time windows).

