AE = adverse event; ALT = alanine aminotransferase; AST = aspartate aminotransferase; CGI-C = Clinician's Global Impression of Change of the patient's relapsing MS; CXR = chest X-ray; DBP = diastolic blood pressure; DIR = double inversion recovery; $DL_{CO} =$ diffusing capacity for the lungs measured using carbon monoxide; eC-SSRS = electronic self-rated version of the Columbia-Suicide Severity Rating Scale; ECG = electrocardiogram; eCRF = electronic case report form; EDSS = Expanded Disability Status Scale; FS = functional system; FSIQ-RMS = Fatigue Symptom and Impact Questionnaire-Relapsing Multiple Sclerosis; INR = International Normalized Ratio; MRI = magnetic resonance imaging; MS = multiple sclerosis; MSFC = Multiple Sclerosis Functional Composite; MTR = magnetization transfer ratio; OCT = optical coherence tomography; PFT = pulmonary function test; PGI-S = Patient's Global Impression of Severity of Fatigue; PI = principal investigator; PK = pharmacokinetics; SAE = serious adverse event; SBP = systolic blood pressure; SDMT = Symbol Digit Modalities Test; WPAI:MS = Work Productivity and Activity Impairment Index: Multiple Sclerosis.

Table 2Visit and assessment schedule (Part 2)

Periods	Name		TREA	IMENT P	ERIOD	FOLLOW-UP		UNSCHEDULED				
	Duration			108 Weeks	-	30 I	Days					
	NT 1	1.1	10	10	14	1.5	16	D1 D2	111 112	I1, I	2,	
	Number	11	12	13	14	15	10	K1, K2,	01, 02,	d1	d15	
	Name	W72	W84	W96	EOT	FU1	FU2	Relapse	Unscheduled	Re-ini	tiation	
Visite									(19)	Day 1 of re- initiation	Day 15 after re-initiation	
VISItS	Time	Week 72	Week 84	Week 96	Week 108 or earlier in case of premature discontinuation (18)	Last study drug intake +15 days	Last study drug intake +30 days	А	ny day between	n Day 1 and EO	S	
	Visit window	\pm 7 days	\pm 7 days	\pm 7 days	\pm 7 days	−1 day, +7days	+7 days (22)	+7 days	NA	NA	$\pm 1 \text{ day}$	
EDSS/FS*		Х	Х	Х	Х		Х	Х	Х			
Relapse* (1)		X(1)<			>X(1)	Х	Х	Х	X (21)			
MSFC*, SDM	T*		Х		Х							
FSIQ-RMS**	(2), PGI-S**, CGI-C *		Х		Х			Х	Х			
SF-36v2**			Х		Х			Х				
Health care re	source utilization* (3)	х	Х	Х	Х			Х				
WPAI:MS**			Х		Х							
Patient preferen	nce questionnaire** (4)					Х						
Chest X-ray*	(5)				Х							
MRI** (6)					Х				Х			
eC-SSRS**					Х							
Concomitant 1	nedications*	Х	Х	Х	Х	Х	Х	Х	Х			
Physical exam	ination*		Х		Х			Х	Х			
Dermatologica	al examination* (7)				Х				Х			
Body weight*					Х				Х			
Body tempera	ture*	х	Х	Х	Х	Х	Х	Х	Х	Х	Х	
SBP/DBP*		Х	Х	Х	Х	Х	Х		Х	X(8)	Х	

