AE = adverse event; ALT = Alanine aminotransferase; AST = aspartate aminotransferase; CGI-C = Clinician's Global Impression of Change of patient's relapsing MS; CNS = central nervous system; DBP = diastolic blood pressure; DL_{CO} = diffusing capacity for the lungs measured using carbon monoxide; DIR = double inversion recovery; eC-SSRS = electronic self-rated version of the Columbia-Suicide Severity Rating Scale; ECG = electrocardiogram; eCRF = electronic case report form; EDSS = Expanded Disability Status Scale; EOS = End-of-Study; EOT = End-of-Treatment; FS = functional system; FSIQ-RMS = Fatigue Symptom and Impact Questionnaire-Relapsing Multiple Sclerosis; FU1 = follow-up visit 1; FU2 = follow-up visit 2; MRI = magnetic resonance imaging; MS = multiple sclerosis; MSFC = Multiple Sclerosis Functional Composite; MTR = magnetization transfer ratio; OCT = optical coherence tomography; PFT = pulmonary function test; PGI-S = Patient's Global Impression of Severity of Fatigue; PI = principal investigator; PK = pharmacokinetics; SAE = serious adverse event; SBP = systolic blood pressure; SDMT = Symbol Digit Modalities Test; WPAI:MS = Work Productivity and Activity Impairment Index: Multiple Sclerosis.

Periods	Name	POST-TREATMENT OBSERVATION PERIOD (PTOP) (to be performed after EOT) Up to 108 Weeks						
	Duration							
Visits	Number	6A, 8A, 9A, 11A,13A	7A, 12A	10A, 14A				
	Name	W12A, W36A, W48A, W72A, W96A	W24A, W84A	W60A, W108A				
	Time	Week 12-36-48- 72-96	Week 24 and 84	Week 60 and 108				
	Visit window	±7 days	±7 days	±7 days				
EDSS/ FS*		Х	Х	Х				
Relapse*(1)			X(1)<	>X(1)				
MRI*				Х				
FSIQ-RMS** (2), PGI-S**, CGI-C *		X (only Week12)	Х	Х				
Concomitant medications*		Х	Х	Х				
Physical examination*				Х				
Dermatological examination* (3)				Х				
SBP/DBP*		Х	Х	Х				
12-lead ECG **				Х				
Body temperature*		Х	Х	Х				
Pulmonary function tests** (4)				X (Week 108 only)				
Hematology/Chemistry** (fasted)			Х	Х				
Urinalysis*			Х	Х				
Pregnancy test*/** (5)		Х	Х	Х				
AEs/SAEs *		Х	Х	Х				

*Data collected in the eCRF

**Electronically transferred to sponsor.

Day 1 (date of randomization visit) is to be used as the reference date for the purpose of calculating the subsequent visit dates (and time windows). If the first PTOP visit windows overlaps with FU1 or FU2 visits, visits and assessments can be combined.

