Once step 1 of the relapse detection has been initiated (whether by subject calling the site, by interview of the subject at scheduled visit, or by scheduled calls from the site to the subject), the final result of the relapse detection and confirmation process will be captured as one of the following 3 outcomes: no relapse, unconfirmed relapse, or confirmed relapse. New or worsened neurological symptoms reported by the subject and for which there is another, better explanation for the subject's current symptoms than an MS relapse will be captured on an AE page.

All MS relapses, whether or not confirmed, must be reported on specific relapse pages of the eCRF. MS relapses and associated symptoms are not to be entered on the AE page of the eCRF with the following exceptions:

- MS relapses with fatal outcome (these must always be recorded as AEs on the AE page in addition to being reported as SAEs).
- MS relapses that, in the view of the investigator, warrant specific notice due to unusual frequency, severity or remarkable clinical manifestations (these should be reported as AEs on the AE page of the eCRF and, if applicable, on the SAE form).

Ponesimod / ACT-128800 **Relapsing multiple sclerosis** Protocol AC-058B301, OPTIMUM Version 7

Confidential

EudraCT 2012-000540-10

Doc No D-18.388

5 December 2018, page 127/376

Flow diagram for the detection and evaluation of relapses Figure 7

** If appropriate (e.g., subject has a fever or an infection which can explain the symptoms, or if there is another and better explanation for the patient's current symptoms than an MS relapse), enter subject's symptoms or diagnosis on the AE page.

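### Health care resource utilization is defined up to Week 108, but its scheduled collection ends at EOT, so totals for subjects who stop study drug early are incomplete

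*Protocol*

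**What the plan says.** Protocol Section 6.4 lists "Health care resource utilization from baseline up to Week 108" and names four components: hospitalizations, length of stay, intensive care admissions for MS relapse, and emergency facility visits for MS. The synopsis repeats this. The Version 7 amendment rationale adds: "It was corrected that health care utilization will be not be displayed by visit".

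Collection is set by the three visit tables:

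- **Table 1**, row "Health care resource utilization* (6)": Weeks 2, 4, 12, 24, 36, 48 and 60.
- **Table 2**, row "source utilization* (3)": Weeks 72, 84, 96, EOT and unscheduled relapse visits (R1, R2, ...). It is blank at FU1 and FU2. The unscheduled columns may fall on any day from Day 1 to EOS.
- **Table 3**, headed "POST-TREATMENT OBSERVATION PERIOD (PTOP) (to be performed after EOT) Up to 108 Weeks": no row for the item.

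Subjects who stop study drug early are not withdrawn. Section 5.1.12 follows them to Week 108 unless consent is withdrawn. The synopsis says of the PTOP: "It consists of an abbreviated schedule of assessments at the time of the originally scheduled 12-weekly visits".

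**The concern.** The endpoint's time window and its collection schedule do not match for one group of subjects. Those who stop early keep attending 12-weekly visits to Week 108, but the resource use page is not scheduled at any of them.

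This matters more for a count than for a score. With a change score, an unmeasured visit is visibly missing. With a number of admissions or days in hospital summed over a fixed window, a period in which nobody asked looks the same as a period without use. Unless the analysis adjusts for it, totals are too low for discontinued subjects. If the arms discontinue at different rates, part of any difference in resource use could reflect how long each arm was asked. Relapses, by contrast, are followed through the PTOP, so relapse and resource results would rest on different observation periods.

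**Working it through.** **1. Window against schedule.** No stated figure has to be reproduced; the check sets the sections side by side.

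| Subject and period | Within the Week 108 window? | Scheduled collection? |
|---|---|---|
| Completer, Day 1 to EOT at Week 108 | yes | yes (Tables 1 and 2) |
| Completer, FU1/FU2 | no, after Week 108 | not needed |
| Early discontinuer, Day 1 to EOT | yes | yes |
| Early discontinuer, FU1/FU2 | normally yes | no (Table 2 blank) |
| Early discontinuer, PTOP visits 6A to 14A | yes | no (no row in Table 3) |

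The gap is therefore confined to early discontinuers.

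**2. What relapse visits still capture.** Table 2 marks the item at relapse visits up to EOS. Under Section 3.1.4, EOS for an early discontinuer is FU2 or the last PTOP visit, whichever is later. Under Section 7.2.2, relapse contacts continue after discontinuation, and a relapse suspected at a contact leads to an unscheduled relapse visit. So some resource use in the PTOP is recorded.

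**3. What relapse visits do not assure.**

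- Section 6.4 does not limit hospitalizations or length of stay to MS. An admission with no relapse visit has no scheduled capture.
- Section 7.2.2 places the EDSS within 7 days of symptom onset and before any corticosteroid treatment. An admission, or most of its length, can follow that visit. On treatment the next scheduled visit could pick it up; in the PTOP none does.
- A relapse identified at a scheduled visit uses that visit's EDSS, so it need not generate a relapse visit.
- The AE pages of Table 3 are only a partial substitute. Section 7.2.2 says "MS relapses and associated symptoms are not to be entered on the AE page of the eCRF", apart from two stated exceptions.

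**4. Size.** The rate of stopping study drug is not stated in the text available, so a range is assumed. Let d be cumulative discontinuation by Week 108 with a constant hazard. The window is T = 108 × 7 / 365.25 = 2.07 years. Mean time on treatment as a share of T is d / (−ln(1 − d)), so the share without scheduled collection is

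1 − d / (−ln(1 − d)).

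- d = 10%: 1 − 0.10/0.1054 = 5.1%
- d = 20%: 1 − 0.20/0.2231 = 10.4%
- d = 30%: 1 − 0.30/0.3567 = 15.9%

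Planned person-time is 1100 × 2.07 = about 2277 person-years, so these shares are about 116, 236 and 362 person-years. They assume every discontinuer stays to Week 108, and they subtract nothing for relapse visits.

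As a hypothetical imbalance, 10% discontinuation in one arm and 20% in the other would leave 5.1% and 10.4% of person-time without scheduled collection, a difference of 5.3 percentage points.

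**The case against.** The strongest reply is that collection does not stop with study drug. Relapse visits reach into the PTOP and carry the resource use page, and they cover the MS-specific components best. This stands. A reader of Table 3 alone might infer that nothing is collected after discontinuation, or that PTOP relapse admissions cannot be recovered; Table 2 read with Section 3.1.4 contradicts both. What remains is incomplete capture, as in step 3.

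Second, an unadjusted total is nowhere prescribed. The amendment rationale says only that results are not shown by visit. Sections 7.6.2, 8.3.2, 8.4.1 and 11.3.5.9 are in the table of contents but were not in the text available, and they or the SAP may set collection details or a time-adjusted rate. This also stands, so the bias is conditional on the analysis. A rate would reduce the bias but would not supply the Week 108 window that Section 6.4 states.

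Third, the PTOP is deliberately abbreviated, and other endpoints described up to Week 108, such as WPAI:MS and SF-36v2, have no PTOP row either. That is fair, but those are by-visit changes, where a missing visit shows as missing. Whether use under later local care belongs in the comparison is a legitimate choice; the wording and the schedule should then make the same one.

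A reader might also size the gap from the sample-size dropout assumption (15% in year 1, 7.5% in year 2), which gives about 13% of person-time. The protocol does not equate dropout with stopping drug: Section 5.1.12 separates the two. If dropout means leaving the study, those subjects have no PTOP visits and an added page recovers nothing from them. Nor do the documents show that discontinuers use more resources, or that the arms will discontinue at different rates. Under any imbalance, time is missing from both arms, not from one.

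**Conclusion.** The mismatch is real and minor. Section 6.4 and the synopsis promise resource use to Week 108, while scheduled collection ends at EOT and only unscheduled relapse visits record it afterwards. Totals to Week 108 are therefore incomplete for early discontinuers. They are too low if analysed without adjustment for time under collection, and the arm comparison could be distorted if discontinuation differs by arm.

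For an assumed 10% to 30% cumulative discontinuation at a constant hazard, about 5% to 16% of planned person-time lacks scheduled collection. The loss of events is smaller to the extent that relapse visits capture them, and the documents do not allow that part to be estimated. This is a pharmacoeconomic endpoint outside the alpha-controlled tests, so the primary analysis, power and type I error are untouched.

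**What to change.** Preferred: add the existing resource use eCRF page to the Table 3 PTOP visits (6A to 14A), worded to ask about use since the last visit. The first PTOP visit then also covers the interval containing FU1 and FU2. The cost is a few minutes at visits the subject already attends.

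If collection stays as it is: restate the endpoint in Section 6.4 and the synopsis as baseline to EOT, expressed per on-treatment subject-year, and leave use recorded at relapse visits after EOT out of the count so that numerator and denominator cover the same time. This costs one line of wording, but the endpoint then says nothing about use after discontinuation.

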6.5 Pharmacokinetic and pharmacodynamic endpoints

6.5.1 Pharmacokinetic endpoints

• Plasma concentrations of ponesimod pre-dose at Weeks 12, 60, and 108 and 3 h post-dose on Day 1 and at Week 12.

6.5.2 Pharmacodynamic endpoints

- Peripheral blood lymphocyte counts pre-dose (absolute and change from baseline counts) by visit up to Week 108
- Change from baseline to EOS vs change from baseline to EOT in lymphocyte counts (absolute and % change)
- Post-treatment lymphocyte recovery at 15 days and 30 days after study drug discontinuation

7 STUDY ASSESSMENTS

All study assessments are performed by a qualified study staff member: medical, nursing, or specialist technical staff, and are recorded in the eCRF, unless otherwise specified. Study assessments performed during unscheduled visits will also be recorded in the eCRF.

If the principal investigator delegates any study procedure/assessment for a subject, e.g., ECG, MRI, blood sampling etc., to an external facility, she/he should inform Actelion to whom these tasks are delegated. The set-up and oversight will be agreed upon with Actelion. The supervision of any external facilities remains under the responsibility of the principal investigator.

Calibration certificates for the following devices used to perform study assessments must be available prior to the randomization of the first subject:

• Temperature measurement devices for study medication storage area and lab sample storage (e.g., freezer).

• Spirometer; in addition, a copy of the calibrations check (syringe check) of the day of measurement must be stored and a log of calibration check results must be maintained at the site [see Section 7.3.5].

- DL_{CO} gas analyzer (if applicable); in addition, a copy of the calibrations of the day of test must be stored and a log of calibration results must be maintained at the site. Frequent testing involving the same healthy subject control (biological quality check) or a DL_{CO} simulator will ensure continuous monitoring of the gas analyzer measurement accuracy over time [see Section 7.3.6].
- ECGs.
- BP monitoring device.
- MRI; in addition, prior to the start of the study, each MRI site must be qualified by MIAC [see Section 7.2.3].

